3.4 Study Time Frame

The duration of the study for each participant will be 31 weeks: 1 week before randomization as eligibility screening and baseline assessment, 6 weeks of treatment period, and 24 weeks of follow up period after the cessation of treatment (Figure 1. Study Design).

[figure not shown]

Figure 1. Study Design

There will be four timepoints of assessment:

Timepoint 1 will be scheduled during weeks -1 as eligibility screening and baseline assessment;

Timepoint 2 will be scheduled at week 6 at the end of treatment period;

Timepoints 3 and 4 will be scheduled at weeks 18 and 30, respectively, during 24-week follow-up period.

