10.3 Compliance Improvement

- (1) Participants should participate in the trial voluntarily, and sign the informed consent.
- (2) Research assistants should record the participants' contact information in detail for the convenience of follow-up.
- (3) Before randomization, researchers should inform the participants that all the cost related to the examination and treatment would be exempted.
- (4) Each participant's participation in the trial should be taken charge of by the same research assistant and outcome assessor throughout the trial. They will explain the contents of notebook to participants, if necessary, remind the participants of their schedule by phone or we-chat, and instruct participants to complete the notebook.
- (5) For participants who have less compliance, we will still follow them up to record outcome measurements through phone or message.

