11.1 Sample Size Calculations

A sample size of 196 participants (98 in each group) was estimated to have provide at least 80% power at a 2-sided significance level of 5% to detect on a between-group difference of 2.5 points in the RMDQ score [23], assuming a standard deviation of 5.5 and a 20% dropout rate.

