6.3.3 Analysis for Primary Outcome

The primary analysis will be conducted a mixed effects model for repeated measures (MMRM). In this model, the observed change from baseline score at each scheduled post-baseline visit will be the dependent variable. The model will include the baseline RMDQ score as a fixed effect, with categorical factors for treatment group (acupuncture and SA), visit and treatment \times visit interactions. The interactions will remain in the model regardless of significance. Treatment group comparisons at each visit will be estimated by differences between least squares (LS) means from the treatment \times visit interaction, with accompanying *P*-values and 95% CIs. An unstructured covariance pattern will be used to estimate the variance–covariance of the within-subject repeated measures. Parameters will be estimated using maximum likelihood with the Newton-Raphson algorithm and using the Kenward–Roger method for calculating the denominator degrees of freedom.

Sensitivity Analyses for the Primary Outcome

Multiple imputation will be used to impute missing values under the missing-at random assumption (MAR). Specifically, 100 imputed data sets will be generated using the fully conditional specification method or regression method with the number of iterations set to 10 for the following variables: group, baseline value and dependent variable. After multiple imputation, each of the hundred multiple imputation datasets will be analyzed using the MMRM model. The overall estimates will be calculated using Rubin's rules. The multiple imputation procedure (PROC MI) in SAS, version 9.4 will be used and *P*-value <0.05 will be considered statistically significant. To address potential center differences, we will incorporate site as either a fixed or random effect in the MMRM model.

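### SAP 6.3.3 names maximum likelihood rather than REML for the primary MMRM; read literally, the week-6 standard error is about 0.7–0.9% too small, so REML should be named

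*Combined protocol and SAP*

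**What the plan says.** SAP 6.3.3 sets out an MMRM for change in RMDQ at the post-baseline visits (weeks 6, 18 and 30). It has baseline RMDQ, treatment, visit and treatment-by-visit terms and an unstructured covariance. On estimation it states: "Parameters will be estimated using maximum likelihood with the Newton-Raphson algorithm". The same sentence adds Kenward-Roger as the "method for calculating the denominator degrees of freedom". On model terms it says "The interactions will remain in the model regardless of significance".

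The estimator carries over to other fits:
- In the multiple-imputation sensitivity analysis, "each of the hundred multiple imputation datasets will be analyzed using the MMRM model".
- For centre differences, "we will incorporate site as either a fixed or random effect in the MMRM model".
- SAP 6.3.4 applies the primary approach to the other continuous outcomes.

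REML, under any of its names, appears nowhere in the protocol or the SAP.

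**The concern.** ML estimates the variances and covariances as if the mean parameters were known, so the variances come out slightly too small. REML allows for the fitted fixed effects, and Kenward-Roger was built on REML. Asking for ML together with Kenward-Roger requests a small-sample correction on top of an estimate that still carries the bias.

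The usual reason to prefer ML is to compare models with different fixed effects by their likelihoods. No such comparison is planned, since the interactions stay in whatever their significance.

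At stake are the P value and confidence interval of the single primary test. The error runs in one direction, towards significance. While the text can be read either way, two programmers can produce two slightly different primary P values, and the choice could be made after the data are seen.

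**Working it through.** **Inputs from the documents.** Protocol 11.1: 196 participants, 98 per arm, difference 2.5, two-sided 5%, 80% power, "assuming a standard deviation of 5.5 and a 20% dropout rate". SAP 6.3.3: three visits and 7 mean parameters (3 visit means, 3 treatment effects, 1 baseline slope).

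**Assumptions.** The documents give no between-visit correlations, so equal correlations of 0.5 and 0.65 are used, with 0 to 0.8 as a wider range. SD 5.5 is taken as the residual SD at each visit. Dropout timing is not stated. Participants have "24 weeks of follow up period after the cessation of treatment", and section 10.3 says: "For participants who have less compliance, we will still follow them up to record outcome measurements through phone or message". Three timings are therefore shown: no loss; cumulative loss of 7/13/20% by weeks 6/18/30; all 20% lost before week 6.

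**The plan's sample size.** The normal formula gives 2 × (1.960 + 0.842)² × (5.5/2.5)² = 75.98, so 76 per arm. The t-test version needs 77, and 77/0.8 = 96.25, so 97 per arm or 194 in total. The stated 196 agrees closely.

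**Rough size of the shortfall.** The ratio of ML to REML standard error is about √((N − p)/N), where p is the number of mean parameters per visit, between 7/3 and 3.
- N = 196: 1 − √((196 − 2.33)/196) = 0.60%, up to 1 − √(193/196) = 0.77%.
- N = 157 (39 lost): 0.75% to 0.96%.

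**Direct fits.** The same simulated null trials (150 per cell) were fitted by ML and by REML, and the Kenward-Roger-adjusted week-6 standard errors compared. ML shortfall:

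| Dropout timing | Correlation 0.5 | Correlation 0.65 |
|---|---|---|
| None | 0.68% | 0.71% |
| 7/13/20% by weeks 6/18/30 | 0.74% | 0.76% |
| All 20% before week 6 | 0.85% | 0.88% |

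The Monte Carlo SE of these means is about 0.01 percentage points or less. A second implementation (Fisher scoring instead of EM) gave 0.69–0.88%; for example, with all 20% lost early at correlation 0.5, 1 − 0.8552/0.8625 = 0.85%. Over correlations 0 to 0.8 the range is 0.60–0.92%. Loss before week 6 moves the figure more (0.68 to 0.85) than correlation does (0.68 to 0.71). Adjusted and unadjusted shortfalls agree to two decimals, so Kenward-Roger does not remove the deficit.

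**P value**, taking the point estimate as the same under both methods:
- No loss, correlation 0.5: P = 0.050 on 196 df is t = 1.9721. Under REML, t = 1.9721 × (1 − 0.0068) = 1.9587 on 194 df, P = 0.0516.
- All 20% lost early, correlation 0.65: t = 1.9752 × (1 − 0.0088) = 1.9578 on 154 df, P = 0.0521.

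That is 0.16–0.21 percentage points of type I error relative to REML.

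**CI width.**
- No loss: SE = 5.5 × √(2/98) = 0.786. The REML width is 2 × 1.972 × 0.786 = 3.10, and ML is 0.02 narrower.
- 78 per arm: SE = 0.881, width 3.48, and ML is 0.03 narrower.

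**Rejection rates in 4,000 null trials.** ML 5.65% against REML 5.45% (no loss, correlation 0.5), and 4.52% against 4.35% (all 20% lost early, correlation 0.65). The paired gaps of 0.20 and 0.17 points (Monte Carlo SE about 0.07) match the calculation. The levels themselves have a Monte Carlo SE of about 0.34 points and are not interpreted.

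**Site as a fixed effect.** With assumed centre sizes of 40/39/39/39/39, blocks of 4 and 6 and no centre effect, the shortfall is 1.36–1.87% at correlations 0.5–0.65, and an ML P of 0.050 corresponds to a REML P of 0.0532–0.0545. Site as a random effect was not computed.

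**The case against.** The strongest reply is that the effect is negligible: 0.02–0.03 RMDQ points of interval width, against a minimal clinically important difference of 2.5. The point estimate, the missing-data assumption and the planned sample size do not depend on it. This is correct, and it limits the point to a minor one.

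The second reply is that no error has been shown. The phrase can be a loose term for likelihood-based fitting, and asking for Kenward-Roger suggests that REML was meant. That is plausible. It is equally a reason to name the estimator, because the literal text says something else, and protocol 11.2 provides for a final SAP before database lock and code breaking.

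Three smaller points also stand:
- The upper end, near 0.9%, needs the whole 20% to be lost before week 6. That is extreme, since poor compliers are still followed.
- The planned power calculation is unaffected, but a slightly liberal test also rejects slightly more often under the alternative: about 0.3 points more with no loss (88.6% to 88.9%) and 0.5 points with 20% lost (80.8% to 81.3%).
- In the multiple-imputation analysis the within-imputation shortfall is about 0.7%, and pooling dilutes it. If 10–20% of the total variance lies between imputations (assumed), about 0.54–0.61% remains.

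The larger site-adjusted figures concern a sensitivity model on which the primary conclusion does not rest.

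**Conclusion.** The concern holds, as a minor one. As written, SAP 6.3.3 specifies an estimator that makes the primary standard error 0.68–0.88% smaller than REML would, at assumed correlations of 0.5–0.65 and across dropout timings from no loss to all 20% lost before week 6. A conclusion could change only if the ML P value fell just under 0.05, with its REML counterpart no higher than about 0.052. The direction and rough size hold across every correlation and dropout pattern examined. Whether ML would actually be fitted cannot be settled from the documents.

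**What to change.** In SAP 6.3.3, replace maximum likelihood with restricted maximum likelihood (REML), and keep the unstructured covariance, Newton-Raphson and Kenward-Roger. State that this applies to the primary MMRM, to its site-adjusted and multiple-imputation sensitivity fits, and to the continuous-outcome MMRMs in 6.3.4. Leave the binomial identity-link models in 6.3.4 as they are. If REML was already intended, the edit only removes an ambiguity. The cost is a phrase in the SAP and one option in the program, with no added data, participants or analyses. It should be settled before code breaking.

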7.4 Permitted and Prohibited Concomitant Treatments

The use of medications or other therapies specific for symptoms of DLSS will be discouraged during this trial. Patients with intolerable pain will be allowed to take 200 mg dose of Celebrex (Pfizer China, Inc.) orally once a day for three consecutive days as rescue medicine with detailed record. We will compare the proportion of subjects using rescue medications between groups. Rescue medicine will be prohibited 48 hours prior to the pain and physical function assessment.

8. Subject Evaluation

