8.2.3 Six-week Treatment Phase

During the 6-week treatment (weeks 1-6), Timepoint of assessment 2 will be scheduled at week 6.

Participants will complete the RMDQ, NRS, SSSQ and HADS at week 6.

Within 5 minutes after treatment (sessions 17 or 18) at the week 6, the success of blinding will be assessed by outcome assessors at hospital.

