6.3.4 Analyses for Secondary Outcome

Efficacy analyses for all secondary outcomes will be performed in the ITT population, without imputation of missing data.

The same approach for the primary outcome will be used in other continuous outcomes such as SSSQ for symptom severity, physical function. Categorical data will be compared between groups using a generalized linear model with a binomial distribution and identity link that will include the same covariate as the MMRM model. In addition to the proportion of participants who were somewhat satisfied and very satisfied based on the satisfaction domain of the SSSQ, we will be analysis use the generalized linear model with the same covariate as the MMRM model. Patients' expectations of acupuncture for general disease and for DLSS, blinding, adherence data will present for descriptive purposes only.

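### The only missing-data sensitivity analysis imputes RMDQ from the same information as the primary MMRM, so for patients with no post-baseline RMDQ it nearly repeats the primary result

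*Combined protocol and SAP*

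**What the plan says.** **Primary analysis (SAP 6.3.3).** This is an MMRM in which "the observed change from baseline score at each scheduled post-baseline visit will be the dependent variable". On covariates: "The model will include the baseline RMDQ score as a fixed effect, with categorical factors for treatment group (acupuncture and SA), visit", plus the treatment-by-visit interaction. Centre is not in this model.

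**Sensitivity analyses (SAP 6.3.3).** One hundred data sets are imputed under missing at random (MAR), by either fully conditional specification (FCS) or the regression method, "for the following variables: group, baseline value and dependent variable". Each is analysed with the MMRM and the results are combined by Rubin's rules. The other sensitivity analysis concerns centre: "we will incorporate site as either a fixed or random effect in the MMRM model". No other missing-data analysis of the primary outcome is planned.

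**Timing (Protocol 8.2.3).** "Timepoint of assessment 2 will be scheduled at week 6". RMDQ is not scheduled between baseline and then; weeks 18 and 30 follow.

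**Data held on a patient lost before week 6.**
- Baseline NRS, SSSQ, HADS and expectancy (Protocol 5.2).
- Centre, the randomisation stratum (Protocol 6.1).
- Rescue use, allowed for "three consecutive days as rescue medicine with detailed record" (Protocol 7.4).
- Demographics, course of disease and previous treatments (Protocol 5.2), and adverse events (Protocol 8.1.2 and 9.1).
- Adherence, of which SAP 6.3.4 says "adherence data will present for descriptive purposes only".

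**The concern.** An MMRM fitted by likelihood is already valid under MAR given its own variables. Imputation that stays within MAR can add something only by conditioning on more than the MMRM does. Here it does not. If the two analyses agree, the report will read as robustness to missing data, although agreement was nearly guaranteed by construction.

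The documents give reason to expect loss linked to symptoms. Protocol 9.2 foresees withdrawal for worsening symptoms. Protocol 7.4 reserves rescue for intolerable pain and plans to compare its use between groups. If patients who are doing badly are lost more often in one arm than in the other, the MMRM and the planned imputation shift together, and nothing in the plan would reveal it. The week-6 NRS, SSSQ and HADS cannot help, because they are missing at the same visit. Data recorded at baseline or before loss can.

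**Working it through.** **1. The plan's own figure.** Protocol 11.1 gives difference 2.5, SD 5.5, two-sided 5%, at least 80% power, 20% dropout and 196 patients (98 per arm).
- Normal approximation: 2 × (1.96 + 0.8416)² × 5.5² / 2.5² = 76 per arm; 76 / 0.8 = 95.
- t-test: 77 per arm; 77 / 0.8 = 96.25, rounded up to 97, so 194 in total.
- With 98 × 0.8 = 78.4 evaluable per arm, t-test power is 80.7%.

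The sample size is sound and is not in dispute. The standard error of the difference is about 5.5 × √(2/78.4) = 0.88.

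**2. Does the planned imputation differ from the primary analysis?** The check used 600 simulated trials per setting, 98 per arm, a true difference of −2.5, SD 5.5, about 20% lost before week 6 with no later data, and 100 imputations. For such patients the likelihood analysis reduces to observed week-6 change on group and baseline. One auxiliary variable had correlation rho with the outcome.

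| Loss depends on the auxiliary | rho | Likelihood | MI as listed | MI plus auxiliary |
|---|---|---|---|---|
| equally in both arms | 0.3 | −2.54 | −2.54 | −2.53 |
| equally in both arms | 0.5 | −2.50 | −2.50 | −2.52 |
| in one arm only | 0.3 | −2.81 | −2.81 | −2.52 |
| in one arm only | 0.5 | −3.00 | −3.00 | −2.51 |

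The mean absolute gap between the first two analyses was 0.03 points, and both standard errors were 0.83 to 0.84. The Monte Carlo error of each mean was about 0.035.

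**3. Size by formula.** Shift = m × rho × SD × D. Here m is the fraction missing, and D is the between-arm difference, in SDs, in the gap on the auxiliary between lost and retained patients. The documents give neither rho nor D. With m = 0.20 and SD = 5.5:
- rho 0.1, D 0.25: 0.20 × 0.1 × 5.5 × 0.25 = 0.03
- rho 0.3, D 0.5: 0.20 × 0.3 × 5.5 × 0.5 = 0.17
- rho 0.5, D 1.0: 0.20 × 0.5 × 5.5 × 1.0 = 0.55

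The shift scales with m, so halving early loss halves it.

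**4. A rescue-use example, all inputs assumed.** Rescue use is 31% (sham) and 21% (acupuncture), and its correlation with week-6 RMDQ is 0.23 to 0.38. With rescue fully known and in the imputation, the estimate is 2.49.
- Odds ratio of loss 4 in sham only, 20% lost: planned variables give 2.32 to 2.20, a shift of 0.17 to 0.29.
- The same odds ratio with 10% lost: shift 0.10 to 0.16. With 5% lost: 0.05 to 0.08.
- Odds ratio 8 in sham only, 25% against 15% lost: 2.18 to 1.97, a shift of 0.31 to 0.52.
- The same mechanism in both arms: 0.01 to 0.15.

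The direction is not fixed. This example shrinks the benefit, while the one-arm case in step 2 enlarges it.

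**5. How much is recoverable.** Rescue records stop when the patient is lost. With rescue counted only if it came before loss (independent, uniform times assumed), rescue alone recovered about 32% to 47% of the shift in the one-arm settings, for example 1.94 to 2.18, and none in the common-mechanism settings. In a further simulation with true value 2.5, baseline auxiliaries plus rescue before loss did better:
- 20% lost: 2.08 to 2.38, so (2.38 − 2.08) / (2.50 − 2.08) = 0.30 / 0.42 = 71%.
- 10% lost: 2.27 to 2.42, so 0.15 / 0.23 = 65%.

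With eight uninformative auxiliaries at 98 per arm, the SDs of the estimate with and without them were 0.877 and 0.884, a difference under 1%.

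**The case against.** The case for leaving the plan alone is substantial:

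- **The affected group may be small.** Weeks 18 and 30 are already in the imputation through the dependent variable. Protocol 10.3(5) keeps poor compliers in outcome follow-up by phone or message. The 20% dropout in Protocol 11.1 is not tied to week 6. This stands: the point concerns only patients with no post-baseline RMDQ, and their number is unknown.
- **The larger figures need one-arm mechanisms that the documents do not supply.** This stands. Even 0.5 points is below the standard error of 0.88, though a systematic shift does not average out as sampling error does.
- **Some auxiliaries are poor.** Rescue use is truncated at loss. Sessions received is nearly a proxy for early loss. With 78 completers mostly at 16 to 18 sessions (assumed), the SD of the predicted arm mean at 6 sessions was 8.0 points, against 0.62 without that term. This stands, and sessions should be left out.
- **The choice of auxiliaries is the analyst's, and the plan can be run as written.** This is true, but it does not answer the point that the analysis as listed has almost no capacity to disagree with the primary one.

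A reader might also infer that leaving centre out contradicts the planned site analysis. The documents do not support that. The imputation matches the MMRM applied to it, and nothing says that the site model will be run on imputed data. Only if it were would imputing without site be uncongenial with it.

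**Conclusion.** The point holds as a cheap improvement to a sensitivity analysis. The planned imputation is not an error, but for patients with no post-baseline RMDQ it almost reproduces the primary estimate (0.03 points apart on average). It cannot show whether loss related to recorded variables matters.

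What it could miss runs from near zero to about 0.3 to 0.5 points, or 12% to 20% of the 2.5-point target (0.3/2.5 and 0.5/2.5). It is near zero if loss depends on these variables equally in both arms or if few are lost before week 6. The upper end needs 20% lost before week 6, a mechanism in one arm only and a fairly predictive auxiliary, and only part of it is recoverable.

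Three stronger readings are not supported:
- That the omitted scales, rescue, sessions and centre are the only extra information. Demographics, course of disease, previous treatments and adverse events are recorded too.
- That the primary estimate is biased. The documents give no early-loss rate by arm and no relation between loss and these variables.
- That adding auxiliaries would settle the missing-data question. They stay within MAR and do not replace an analysis that departs from it.

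**What to change.** In SAP 6.3.3, before unblinding (Protocol 11.2 already requires a final SAP before code breaking):

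1. Choose FCS, removing the open choice between FCS and regression.
2. List the imputation variables: group, baseline RMDQ, RMDQ change at weeks 6, 18 and 30, centre, baseline leg NRS, baseline SSSQ symptom severity and physical function, baseline HADS, expectancy, and any rescue use recorded up to week 6 or loss, whichever comes first.
3. Impute within arm, or use a group-by-rescue term, if the model converges. State the fallback in advance.
4. Do not include number of sessions received.
5. Report, by arm, how many patients have no post-baseline RMDQ, so that readers can judge how much rests on the imputation.

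The primary MMRM, and the MMRM fitted to the imputed data, stay as they are.

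**Cost.** SAP wording and a longer variable list. Neither schedule of evaluations has a row for rescue use, so its data field should be confirmed. The main downside is model size. Within an arm, the baseline and rescue terms come to about 14 coefficients: RMDQ 1, NRS 1, SSSQ 2, HADS 1 as a single score, rescue 1, centre 4, and expectancy 4 if both three-category questions enter. That is against about 78 completers, so a convergence check and a short list are needed.

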6.3.4 Analyses for Secondary Outcome

Efficacy analyses for all secondary outcomes will be performed in the ITT population, without imputation of missing data.

The same approach for the primary outcome will be used in other continuous outcomes such as SSSQ for symptom severity, physical function. Categorical data will be compared between groups using a generalized linear model with a binomial distribution and identity link that will include the same covariate as the MMRM model. In addition to the proportion of participants who were somewhat satisfied and very satisfied based on the satisfaction domain of the SSSQ, we will be analysis use the generalized linear model with the same covariate as the MMRM model. Patients' expectations of acupuncture for general disease and for DLSS, blinding, adherence data will present for descriptive purposes only.

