9.2 Subject Withdrawals

Participants may withdraw from the trial at any time at their own discretion; the investigator may also determine whether it is in the best interest of subjects to withdraw from the trial due to worsening of symptoms, or the occurrence of serious AEs.

10. Administrative Responsibilities

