5.1.2 Secondary Outcomes

Secondary outcomes will include the following:

- (1) Changes in the RMDQ score from baseline to weeks 18 and 30;
- (2) The proportion of participants having at least 30% and 50% reductions in the RMDQ score from baseline to weeks 6, 18, and 30;
- (3) Changes in the average pain scores for the buttocks and/or legs when walking, standing, or extending the back as measured by the NRS in the previous 1 week from baseline to weeks 6, 18, and 30.

The NRS is a concise scale for assessing pain that is completed by the participants themselves. NRS scores range from 0 to 10 with 11 grades, and higher scores indicate greater pain [28, 29]. Two scales including one for measuring buttock and/or leg pain and another for measuring low back pain will be used (participants should answer with the average score for the previous 1 week). The degree of pain in the bilateral legs may be different, and data collection will be based on the degree of pain in the leg with more severe pain;

(4) The proportion of participants having at least 30% and 50% reductions from baseline in the average pain scores for the buttocks and/or legs when walking, standing, or extending the back, as measured by the NRS for the previous 1 week at weeks 6, 18, and 30;

(5) Changes in the average pain score for the lower back when walking, standing, or extending the back, as measured by the NRS for the previous 1 week from baseline to weeks 6, 18, and 30;

(6) Changes in the mean scores of the SSSQ for symptom severity and physical function from baseline to weeks 6, 18, and 30 and scores on the SSSQ satisfaction subscale at weeks 6, 18, and 30.

The SSSQ is a short outcome measure for symptoms and functions [30]. The SSSQ consists of 18 questions and three domains including symptom severity, physical function, and satisfaction with the degree of treatment. The scores for all three domains are calculated by taking the total score for the domain and dividing it by the number of answered questions, and if more than two items are missing, the scale scores for that domain are considered missing.

Six questions in the symptom severity domain assess pain of the back, buttocks, legs, or feet

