as well as pain frequency, numbness, and weakness with scores ranging from 1 to 5, while one question assesses balance with possible scores of 1, 3, and 5. Higher scores indicate worse symptoms. The physical function domain assesses walking distance and ability to walk for pleasure, shopping, and getting around the house or apartment and from the bathroom to the bedroom. This domain has five questions with scores ranging from 1 to 4, and higher scores indicate less satisfaction. The satisfaction domain has four categories (very satisfied, somewhat satisfied, somewhat dissatisfied, and very dissatisfied) with a score range of 1–4 [31, 32].

(7) The proportion of participants who are somewhat satisfied and very satisfied based on the satisfaction domain of the SSSQ at weeks 6, 18, and 30;

According to satisfaction domain of the SSSQ, patients scoring 1.5-2.5 points are regarded as somewhat satisfied with the therapy, and those scoring 1.5 points or lower are regarded as very satisfied with the therapy [33].

(8) Changes in the HADS score from baseline to weeks 6, 18, and 30.

The HADS is validated and standardized for measuring the state of anxiety and depression [34, 35]. The HADS has two subscales with 14 items (7 items each), and a total score range of 0–21 with a range of 0–3 for each item. A score of ≥ 8 indicates the presence of anxiety and/or depression.

(9) Expectancy of acupuncture

Expectancy of acupuncture will be recorded at baseline. Participants will be required to answer two questions: “In general, do you believe acupuncture is effective for treating the illness?” and “Do you think acupuncture will help to improve your symptoms of DLSS?”

(10) Blinding assessment

Patients will be asked to answer the following questions after treatment (sessions 17 or 18) within 5 min: “Do you think you have received traditional acupuncture over the past 6 weeks?” The patients can answer “yes” or “no.”

(11) Safety assessment

Adverse events (AEs) related to acupuncture include severe pain, needle breakage, fainting, local hematoma, localized infection, and post-acupuncture discomfort with symptoms such as nausea, vomiting, palpitation, dizziness, headache, anorexia, and insomnia during the treatment period. AEs irrelevant to the treatment will also be recorded in detail throughout the trial.

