6.2 Statistical Analysis Set

The efficacy analyses will be done on the intention-to-treat (ITT) population, which will include all participants who will be randomized according to randomized treatment assignment. The safety analysis will be done on the safety population, which will include the ITT participants who received any treatment.

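### SAP 6.3.4 analyses the responder and satisfaction proportions on observed cases only, with no missing-data sensitivity analysis

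*Combined protocol and SAP*

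**What the plan says.** SAP 6.2 bases efficacy on the ITT set, "which will include all participants who will be randomized according to randomized treatment assignment". SAP 6.3.4 then sets the rule for every secondary outcome: "Efficacy analyses for all secondary outcomes will be performed in the ITT population, without imputation of missing data". For binary outcomes it adds: "Categorical data will be compared between groups using a generalized linear model with a binomial distribution and identity link", with the covariate used in the MMRM. Satisfaction is handled with the same type of model.

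The outcomes concerned are listed in SAP 5.1.2: "The proportion of participants having at least 30% and 50% reductions in the RMDQ score from baseline to weeks 6, 18, and 30"; the corresponding 30% and 50% reductions in buttock or leg pain on the NRS; and "The proportion of participants who are somewhat satisfied and very satisfied based on the satisfaction domain of the SSSQ at weeks 6, 18, and 30".

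SAP 6.3.3 plans an MMRM for the primary outcome and, as a sensitivity analysis of that outcome only, 100 multiply imputed data sets under missing at random. SAP 6.3.4 extends the MMRM to the other continuous outcomes.

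On loss of data, Protocol 11.1 plans for 20% dropout. Under Protocol 9.2 participants may leave at their own wish, or the investigator may decide that they should "withdraw from the trial due to worsening of symptoms, or the occurrence of serious AEs". Protocol 10.3 says: "For participants who have less compliance, we will still follow them up to record outcome measurements through phone or message". Protocol 8.2.4 lets participants mail in the week 18 and week 30 questionnaires.

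**The concern.** A binomial model fitted without imputation cannot use a record whose response is missing. A participant with no RMDQ, NRS or SSSQ satisfaction score at a visit therefore drops out of that visit's comparison, and the effective denominator is those observed, not those randomised.

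The continuous outcomes are better protected. The MMRM uses a participant's scores from other visits, so it remains valid when dropout depends on those observed scores. The binary model as described adjusts only for group and the baseline covariate and discards the scores from other visits. The primary outcome also has a multiple-imputation check, and the binary outcomes have no missing-data check at all.

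What is at stake is how readers judge benefit to patients. SAP 5.1.1 presents the 30% and 50% RMDQ reductions as its thresholds for clinically meaningful improvement. If participants who leave do worse than those who stay, the reported proportions are too high. If the arms lose different numbers, the difference between them is shifted as well.

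**Working it through.** **Inputs from the documents.** Protocol 11.1: 98 per arm, difference 2.5, SD 5.5, at least 80% power, two-sided 5%, 20% dropout. The documents give no expected responder or satisfaction rates and no dropout split by arm.

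**The plan's own figure.** With a two-sample t-test, 2.5/5.5 at 80% power needs 76.95, so 77 per arm. Then 77/0.8 = 96.25, so 97 per arm and 194 in total, against the stated 196. The normal approximation gives 76 per arm, 76/0.8 = 95, and 190 in total. With 98 × 0.8 ≈ 78 completers per arm, power is 80.5% (t) or 81.0% (normal). The stated size is consistent with its inputs, so 20% is a fair planning value for missing data: about 20 of 98 per arm.

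**Formula.** Let p be the completer proportion, d the fraction lost, and f the fraction of those lost who are failures, the rest responding at the completer rate. The proportion among all randomised is

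p(1 − d) + d(1 − f)p = p(1 − d·f).

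The observed-case analysis reports p. It is too high by the factor 1/(1 − d·f), which is 1/0.8 = 1.25 when d = 20% and f = 1. An observed 50% would then correspond to 40% of those randomised.

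**Effect on the difference.** Assumed completer rates are 60% on acupuncture and 45% on sham, so the observed-case difference is always 15 points. The splits by arm and the values of f are also assumptions.

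| Lost, acupuncture / sham | f = 1 (worst case) | f = 1/2 | f = 1/4 |
|---|---|---|---|
| 20% / 20% | 48.0 − 36.0 = 12.0 | 54.0 − 40.5 = 13.5 | 57.0 − 42.75 = 14.25 |
| 20% / 10% | 48.0 − 40.5 = 7.5 | 54.0 − 42.75 = 11.25 | 57.0 − 43.9 = 13.1 |
| 10% / 20% | 54.0 − 36.0 = 18.0 | 57.0 − 40.5 = 16.5 | 58.5 − 42.75 = 15.75 |

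In the second row, for example, f = 1/2 gives 60 × (1 − 0.20 × 0.5) = 54.0 and 45 × (1 − 0.10 × 0.5) = 42.75. The last two rows lose 15% on average, less than the plan allows for. With f = 0 there is no distortion in any row.

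**Is there another denominator rule?** SAP 6.2 says who is included and under which assignment. SAP 6.3.1 asks for counts of missing values. The SSSQ rule in SAP 5.1.2 deals with missing items within a domain, not missing visits. Protocol 10.3 concerns follow-up of less compliant participants. None says how a participant with no score at a visit is counted in a binary outcome.

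**The case against.** The strongest reply is that this is a disclosed observed-case analysis of secondary outcomes. SAP 6.3.4 states the absence of imputation in the same sentence as the ITT label, SAP 6.3.1 requires missing counts, and the RMDQ scores behind the responder definition are analysed by MMRM at every visit. This stands in part. A reader might infer that the ITT label is false or that SAP 6.2 and 6.3.4 contradict each other. They do not, because 6.2 sets no missing-data rule. Disclosure does not, however, supply a check on the result.

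A reader might also infer that participants withdrawn for worsening are known non-responders by the trial's own definition. The documents do not support that. Response is defined at weeks 6, 18 and 30, and the RMDQ in Protocol Appendix 2 asks about the day of completion, so worsening at one time does not settle status months later. Satisfaction is a separate question, and leaving by choice or for a serious AE does not imply non-response.

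Nor is withdrawal the same as a missing score. The documents do not say whether withdrawn participants are still assessed; telephone follow-up and mailed questionnaires could retain some of them.

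Finally, the reference to the MMRM covariate might be read as one repeated-measures binomial model across visits. Even so, no within-subject correlation or likelihood structure is given that would provide the protection the MMRM has.

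**Conclusion.** The point holds for the binary secondary outcomes. As written they are observed-case analyses, with neither the MMRM's use of other visits nor any missing-data sensitivity analysis. The proportions may be too high, and the between-arm difference can move either way.

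The size cannot be determined from the documents. It depends on how many participants lack a score, how many of those are failures, and how losses divide between arms. In the illustration with 20% and 10% lost, a 15-point difference becomes about 11 to 13 points when a half to a quarter of dropouts are failures. The 7.5-point result treats every dropout as a failure. A reader might infer from it that the reported effect would be halved, but it is only the worst case for that assumed split. Nothing in the documents indicates which arm would be favoured.

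The primary MMRM, its imputation analysis and the sample size are not affected. This should be changed, but it does not threaten the main conclusion.

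**What to change.** In SAP 6.3.4, replace the no-imputation rule for the binary outcomes as follows.

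- **RMDQ responders:** derive status at weeks 6, 18 and 30 from the 100 imputed data sets already planned in SAP 6.3.3.
- **NRS responders:** impute the scores in the same way and derive status from them.
- **SSSQ satisfaction:** the 6.3.3 imputation model cannot be copied, because satisfaction is scored only after treatment and has no baseline value. Impute it from group, its other visits and the RMDQ and NRS scores.
- **Analysis:** fit the planned binomial model to each data set, combine by Rubin's rules, and report with all randomised participants as the denominator.
- **Sensitivity analyses:** keep the observed-case result. Add an analysis in which participants with no value at the visit, who left the trial for worsening symptoms or a serious AE (the reasons in Protocol 9.2), count as non-responders or not satisfied. Record the reason for withdrawal so that this can be done.

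The last analysis is needed because imputation under missing at random draws mainly on other visits and adds little for someone with no score after baseline. It belongs in a sensitivity analysis because the failure rule is itself debatable.

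The cost is SAP wording and modest programming, and the reported proportions may be somewhat lower. Protocol 11.2 has the final SAP approved before database lock and code breaking, so the rule should be settled by then.
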